## 3 Project arrangements, method selection and analyses

### 3.1 Patients

This is a longitudinal prospective cohort-study intending to include at least 1000 patients with LBBB from University Hospital of North Norway Tromsø and Harstad, Akershus University Hospital, Lørenskog, Oslo University Hospital, Rikshospitalet, Haukeland University Hospital, Bergen and Nordlands Hospital, Bodø, over a 2-year inclusion period.

Information about present and previous diseases, medication, surgical- or invasive treatment, PM, ICD or CRT implantation, clinical examination and present and previous echocardiographic imaging and blood samples (Hb, Thrombocytes, CRP, Kreatinine, eGFR, Urate, HbA1C, Cholesterol, ProBNP, Troponins, ALAT and Ferritin) will be accessed by the patient's journal.

All prospective study participants will answer one customized and two standardized (EQ5D and HeartQoL) questionnaires. They will undergo general clinical investigation comprising height and weight measurements, baseline ECG, blood samples when not found in the patient's journal, standardized BP measurements and echocardiography with a 3 minutes- hand-grip test at baseline and in a 18 month follow-up study.

Clinical outcome data including death and hospital admissions due to heart failure and CRT implantation will be assessed after 3 and 5 years (eventually after 10 and 15 years) by linkage to data from the patient's clinical records through access to Norwegian Patient Registry (Norsk pasientregister (NPR)), Norwegian Causes of Death Registry (Dødsårsaksregisteret) and Norwegian Cardiovascular Disease Registry (Hjerte- og karregisteret).

St Olavs Hospital, Trondheim, might provide retrospective patient data with echocardiography loops, where outcome-data will be extracted from the same registries.

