### 3.10 Statistical power

It is unknown how high the percentage in this study population will be who suffer from deterioration of LV function. Therefore, a pilot-study on the first 100 study-subject of the different subgroups will be performed in order to calculate the power of the final population size. Pilot participants will be included into the final study population. Assuming different proportions of 5%, 10%, 20% and 30% of patients with deteriorating ventricular function, a difference in septal or global strain between at 5% at a SD of  $\pm 6\%$  the sample size needed for hypothesis 1 in each subgroup will be 220, 129, 73 or 57, respectively for a two-sided test and a Type I error of 0.05.

For calculation of hazard-ratios between patients with against without deterioration of LV function for the primary outcome variable: hospital admission due to CVD, assumed that 5% of all patients either

deteriorate function and the presence of decreased segmental work indicates at least a relative risk of 1.8, at an alpha of 0.05 with 500 patients included, the statistical power will be 82%.

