### 3.11 Statistics

Patients with deteriorating myocardial function will be identified by increasing proBNP by more than 10%, increasing NYHA class, increasing diastolic volume by more than 10% and/or decreasing EF by more than 5%. ANOVA will be used to compare parameters between patients with deteriorating myocardial function and those with unchanged clinical condition after one year. ROC curve analysis will serve to find the ideal cut-off values for continuous variables and assessing sensitivity and specificity of the tests. Univariate and multivariate logistic regression tests will be performed in order to identify the most powerful parameters predicting development of heart-failure with hospital admissions as primary outcome and predicting death (or transplantation) as secondary outcome.

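### Section 3.11 chooses each cut-off and judges it in one ROC analysis, so the reported accuracy, mainly sensitivity, will be too high

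*Protocol*

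**What the plan says.** The sentence at issue is in Protocol section 3.11: "ROC curve analysis will serve to find the ideal cut-off values for continuous variables and assessing sensitivity and specificity of the tests". The next sentence turns to predictors: "Univariate and multivariate logistic regression tests will be performed in order to identify the most powerful parameters predicting development of heart-failure", with hospital admission as primary outcome and death or transplantation as secondary outcome.

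On the sample, section 3.1 says "This is a longitudinal prospective cohort-study intending to include at least 1000 patients with LBBB". Section 3.10 calls the proportion who will deteriorate unknown and works through four cases: "Assuming different proportions of 5%, 10%, 20% and 30% of patients with deteriorating ventricular function". For these it gives subgroup sizes of "220, 129, 73 or 57", based on a strain difference of 5 with SD 6.

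No section names pre-fixed cut-offs, a split sample, resampling, shrinkage or a validation cohort. The pilot is not a separate sample either: "Pilot participants will be included into the final study population". The retrospective Leuven data (section 3.2) and the possible St Olavs data (section 3.1) are given no validation role. Blinding of the strain readers to outcome (section 3.12) protects the measurements but not the choice of cut-off.

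**The concern.** The cut-off that looks best in a sample fits that sample's chance pattern as well as the real difference. If sensitivity and specificity are then read off at that cut-off in the same patients, they overstate what new patients would show. The sensitivity estimate suffers most when few patients deteriorate, because it rests on those few.

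This is more than a detail left to a statistical analysis plan. Section 3.11 assigns selection and assessment to the same analysis, and carrying that out as written gives an upward-biased number.

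The stakes lie in the study's purpose. Section 1.7 wants risk algorithms and a more specific selection of patients for treatment, section 2.1 hypothesises that the new measures substantially improve prediction, and section 4.2 foresees clinical use. Optimistic accuracy would favour that hypothesis even where true performance is modest.

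**Working it through.** **Inputs from the protocol.** Strain difference 5, SD 6, two-sided alpha 0.05, proportions deteriorating 5, 10, 20 and 30%, and subgroup sizes 220, 129, 73 and 57 (all section 3.10). Cohort of at least 1000 (section 3.1).

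**Assumptions.** Normally distributed marker; ideal cut-off taken as the one maximising Youden's J = sensitivity + specificity - 1; outcome for the ROC analysis taken as deterioration.

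**The plan's own figures.** The protocol states no sensitivity, specificity or cut-off, so none can be reproduced. The subgroup sizes can be checked, to see what they count. Section 3.10 states no power for them; at an assumed 80%, total N = (1.96 + 0.8416)² × (6/5)² / [p(1-p)].
- p = 5%: 7.849 × 1.44 / 0.0475 = 237.9.
- p = 10, 20 and 30%: 125.6, 70.6 and 53.8.
- With the t distribution: 240, 128, 73 and 56.

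The stated 129, 73 and 57 are therefore totals at about 80% power. The stated 220 gives about 76.5%. That mismatch is a separate matter, and nothing below depends on it.

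**Best attainable accuracy.** The standardised difference is 5/6 = 0.83. With the cut-off at the true optimum, midway between the means, sensitivity = specificity = Φ(0.417) = 0.66, so J = 2 × 0.66 - 1 = 0.32. A mean apparent J above 0.32 is optimism.

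**Simulation.** In each run I draw both groups, pick the cut-off with the largest J, and record its apparent accuracy. The true accuracy of that cut-off in new patients is then Φ(0.833 - c) for sensitivity and Φ(c) for specificity. Entries are means over 4000 to 6000 runs, apparent v true.

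| Deteriorating v not | Sensitivity % | Specificity % | J | Excess J |
|---|---|---|---|---|
| 50 v 950 (5% of 1000) | 70.2 v 64.1 | 67.1 v 66.8 | 0.37 v 0.31 | 0.06 |
| 100 v 900 (10%) | 68.7 v 64.8 | 67.0 v 66.5 | 0.36 v 0.31 | 0.04 |
| 200 v 800 (20%) | 67.7 v 65.3 | 66.9 v 66.3 | 0.35 v 0.32 | 0.03 |
| 300 v 700 (30%) | 67.2 v 65.4 | 67.0 v 66.3 | 0.34 v 0.32 | 0.03 |
| 11 v 209 (5% of 220) | 75.7 v 61.3 | 68.5 v 67.8 | 0.44 v 0.29 | 0.15 |
| 13 v 116 (10% of 129) | 74.6 v 62.0 | 68.7 v 67.3 | 0.43 v 0.29 | 0.14 |
| 15 v 58 (20% of 73) | 73.7 v 62.7 | 69.6 v 66.7 | 0.43 v 0.29 | 0.14 |
| 17 v 40 (30% of 57) | 73.8 v 64.2 | 69.4 v 65.3 | 0.43 v 0.30 | 0.14 |

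Two things follow. In the full cohort the excess lies almost wholly in sensitivity: about 6 points at 5% deteriorating, falling to about 2 at 20-30%. At the stated subgroup sizes the excess in J hardly changes across the four proportions, because the smaller subgroups go with the higher proportions and the number deteriorating stays between 11 and 17.

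**Predictor selection.** The direction is the same, but the size cannot be taken from the protocol. As an illustration only, assume 20 candidate markers of 0.3 SD each and 1000 patients, and take the best one. J is then 0.29 v 0.11 at 5% deteriorating, 0.24 v 0.11 at 10% and 0.20 v 0.12 at 30%. For one such marker chosen in advance it is 0.18 v 0.11, 0.17 v 0.11 and 0.15 v 0.11.

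**The case against.** The strongest reply is that section 3.11 only names ROC analysis for two purposes. It does not say that both are done in the same patients, that the uncorrected figure will be reported, or that no correction is made, and an unseen analysis plan could add internal validation. It is true that same patients is a reading, not a statement. But it is the plain reading, no other sample is set aside, and internal validation added later would amend the sentence, not fill it in.

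Several stronger readings are tempting and should not be drawn.
- **That sensitivity will be overstated by about 14 points.** That is the case of 11 v 209. It needs cut-offs derived per subgroup, which the protocol does not announce, and the lowest of its four proportions. Deterioration in sections 3.4 and 3.11 is a broad composite, so a higher proportion is quite possible.
- **That specificity is equally inflated.** In the full cohort the excess is under 1 point. It reaches about 3 to 4 points only in the two smallest subgroups.
- **That the regression will find noise predictors at a calculable rate.** The protocol sets no p-value screen and no candidate count, and promises no AUC for the model. The blood tests in section 3.1 ("Hb, Thrombocytes, CRP, Kreatinine, eGFR, Urate, HbA1C, Cholesterol, ProBNP, Troponins, ALAT and Ferritin") are listed as data collected, not as candidate predictors, and proBNP is itself part of the deterioration definition.
- **That the logistic models will have only 50 events in 1000 patients.** The proportions used above are for deteriorating function, whereas those models predict admission and death or transplantation.

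**Conclusion.** The point holds, in limited form. As written, section 3.11 will give accuracy that is too high, and the direction is not in doubt. For one marker at the plan's own effect size in 1000 patients, the overstatement of sensitivity runs from about 6 points (5% deteriorating) to about 2 points (20-30%), with specificity barely affected. It becomes material, at about 0.14-0.15 in Youden's J, if cut-offs are derived in subgroups of 57 to 220. Using the same data "in order to identify the most powerful parameters predicting development of heart-failure" adds optimism of unknown size, which grows with the number of candidates and shrinks with the number of events.

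The figures rest on a normal marker, a Youden-optimal cut-off and deterioration as the outcome. The data themselves remain valid; only the accuracy read from them is affected. The change should be made, but it does not call the study into question.

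**What to change.** Add a short paragraph to section 3.11 stating:
- how the ideal cut-off is defined (for example, maximum Youden index);
- that cut-off choice and any predictor selection are repeated in full within each bootstrap resample, or within each cross-validation fold;
- that optimism-corrected sensitivity and specificity are the main reported figures, with apparent values given only beside them.

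Fixing the cut-offs in advance, or reserving a separate cohort for validation, would serve the same end. A penalised regression model is one option for the predictor step, but this point does not require it.

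The cost is some computing and reported accuracy that looks less favourable. No extra patients, visits or measurements are needed.

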## 1.2 Prognosis

To date there is no consensus on LBBB-related prognosis as study results are clearly influenced by study design, population size, selection criteria and age (21). In 1979 the Framingham Study (4209 subjects, 55 with LBBB) (6) showed a clear association between LBBB and main cardiovascular diseases, such as hypertension, cardiac enlargement and CAD. Coincident with or subsequent to the detection of LBBB, 48% of these individuals developed congestive heart failure. Within 10 years from LBBB detection, cardiovascular mortality was 50% and at 18 years follow-up only 11% of subjects with LBBB remained free of detectable cardiovascular abnormalities. Several studies showed that once a LBBB is established, the prognosis worsens with age, established CAD or congestive heart failure (3,5,7,22,23). In patients with acute myocardial infarctions with LBBB, 30 days mortality, in-hospital death and 1 year's mortality were reported to be substantially increased (3,22,24,25).

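### Section 3.11 fixes logistic regression for hospital admission over years of follow-up, with no rule for patients who die without one; coding them as not admitted or excluding them both distort marker effects

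*Protocol*

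**What the plan says.** Section 3.11 chooses the model: "Univariate and multivariate logistic regression tests will be performed in order to identify the most powerful parameters". The outcomes are "predicting development of heart-failure with hospital admissions as primary outcome and predicting death (or transplantation) as secondary outcome", so death stands apart from the admission outcome.

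Section 3.1 says that the registry outcomes, which include death and heart-failure admission, "will be assessed after 3 and 5 years (eventually after 10 and 15 years").

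Section 3.10 plans the power of the same kind of outcome on another scale. It begins "For calculation of hazard-ratios between patients with against without deterioration of LV function" and continues "for the primary outcome variable: hospital admission due to CVD". The effect size there is that "the presence of decreased segmental work indicates at least a relative risk of 1.8".

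The protocol states no composite of admission and death, no censoring rule and no competing-event rule. It does not say how a death without admission is coded, or to which time point the logistic model refers.

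**The concern.** A logistic model needs a yes or a no for every patient at a fixed horizon. A patient who dies unadmitted has to be forced into that scheme in one of two ways:

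- **Coded as not admitted.** This is what a plain yes/no variable from an admissions registry gives. The patient then shares an outcome class with a stable survivor.
- **Left out.** The analysis is then conditioned on not dying first, which is itself related to the marker.

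Section 3.11 uses these models to pick the strongest predictors, and section 1 wants to separate high-risk from low-risk patients. If a marker's apparent effect on admission depends on how strongly it also predicts death, the ranking of markers is affected. Deaths should be expected. Section 1.2 reports for one cohort "Within 10 years from LBBB detection, cardiovascular mortality was 50" per cent, and section 3.7 excludes short life expectancy only when its cause is non-cardiovascular.

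**Working it through.** **The plan's own figure.** The one number stated for this outcome is the 82% power in section 3.10 (500 patients, relative risk 1.8, 5%, alpha 0.05). A proportional-hazards formula gives Φ(√(500 × 0.05 × 0.95) × ln 1.8 − 1.96) = Φ(2.86 − 1.96) = 81.7%. This matches, but only if all 500 patients count as events. Nothing below depends on it. It does show that 82% can be reached from a hazard-ratio calculation.

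**Inputs**
- Death hazard d: if the 50% at 10 years in section 1.2 is read as a constant hazard, d = ln 2 / 10 = 0.069 per year. Range tried: 0.02 to 0.12 (assumption).
- Admission hazard h: not in the protocol. Assumed 0.03 per year; range tried 0.010 to 0.065.
- Marker effect on admission: hazard ratio 1 (none) or 1.8, the only effect size in section 3.10.
- Marker effect on death: hazard ratio 1 to 5 (assumption).

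**Formulas, constant hazards, horizon T**
- Alive and unadmitted: S = exp(−(h + d)T)
- Admitted by T: F = h/(h + d) × (1 − S)
- Dead without admission: 1 − F − S
- Odds if deaths are coded as not admitted: F/(1 − F)
- Odds if deaths are excluded: F/S
- Odds for admission or death: (1 − S)/S

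**Marker-negative patients at 5 years.** S = exp(−0.0993 × 5) = 60.9%. F = 0.03/0.0993 × 39.1% = 11.8%. Dead without admission: 27.3%.

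**Marker-positive patients at 5 years, and odds ratios against marker-negative**

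| Admission HR | Death HR | F | S | OR, deaths = not admitted | OR, deaths excluded | OR, admission or death |
|---|---|---|---|---|---|---|
| 1 | 2 | 10.1% | 43.0% | 0.84 | 1.21 | 2.06 |
| 1 | 3 | 8.8% | 30.4% | 0.72 | 1.48 | 3.55 |
| 1.8 | 1 | 20.2% | 54.0% | 1.88 | 1.92 | 1.33 |
| 1.8 | 1.8 | 17.8% | 40.9% | 1.62 | 2.25 | 2.25 |
| 1.8 | 3 | 15.1% | 27.0% | 1.32 | 2.87 | 4.21 |

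For row 1: (0.101/0.899)/(0.118/0.882) = 0.84. For row 4: (0.178/0.822)/(0.118/0.882) = 1.62. The reference of 1.88 is the same marker with no effect on death (row 3).

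**Range for a marker that raises only death, 5 years, deaths coded as not admitted.** Over both hazard ranges the odds ratio runs from 0.95 to 0.74 at death HR 2, and from 0.90 to 0.58 at death HR 3. It stays below 1 throughout.

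**When does a real admission effect vanish?** With admission HR 1.8, h = 0.03 and d = 0.069, the odds ratio falls to 1 at a death HR of about 7.4 at 3 years, 4.9 at 5 years, 3.0 at 10 years and 2.4 at 15 years. Over death hazards of 0.12 down to 0.02, the 5-year threshold runs from 3.4 to 13.7.

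**The case against.** **The coding is not in the text.** A reader might infer that section 3.11 counts unadmitted deaths as event-free. It does not say so, and both the coding and the horizon are details that an analysis plan may settle. This stands, and the point is worded conditionally for that reason. It does not remove the point: the choice of logistic regression is already made, and both ways of coding admission alone distort the marker effect, in opposite directions.

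**Not every marker of early death looks neutral or protective.** A reader might also infer this, and the figures do not support it. Apparent protection needs a marker with little or no effect on admission. At the protocol's effect size of 1.8 on both outcomes the odds ratio is reduced but stays well above 1, and cancelling it at 5 years takes a death hazard ratio near 4.9.

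**Death is analysed.** The same sentence of section 3.11 models death or transplantation, and section 3.5 lists mortality. A marker of death would show there. This is true, but it does not repair the ranking of predictors for admission.

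**The size of the problem group is unknown.** At a constant hazard, 50% at 10 years implies 19% dead by 3 years and 29% by 5 years. These are upper-end illustrations. The figure comes from 55 subjects with LBBB in a study reported in 1979 and covers all cardiovascular deaths, not only deaths before an admission. Section 1.2 adds that 48% developed heart failure, so many may have been admitted first.

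**For prediction, the lower absolute risk is real.** With deaths coded as not admitted, the model compares the actual cumulative incidence of admission, and a competing-risk cumulative incidence curve would show the same 11.8% against 10.1%. This also stands. The objection is to reading that contrast as the marker's effect on heart failure.

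**Conclusion.** The point holds in conditional form and should be corrected. Section 3.11 fixes a model without a time axis or censoring for an outcome collected over years, keeps death out of that outcome, and gives no rule for deaths without admission.

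At 5 years, with h = 0.03 and d = 0.069 per year, coding these deaths as not admitted lowers the odds ratio from 1.88 to 1.62 when both hazard ratios are 1.8. For a marker that raises only death, it gives 0.84 to 0.72 at death hazard ratios of 2 to 3 (0.95 to 0.58 over the ranges tried). Excluding the deaths gives 1.21 to 1.48 for that marker. The distortion is smaller at 3 years and larger at 10 and 15, but the longer follow-up is only a possibility.

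The direction under each coding follows from the method. The size rests on assumed constant hazards, an admission rate that the protocol does not give, and a mortality figure from a small, old cohort. The weight also depends on the rank of admission, which sections 3.10 and 3.11 call primary while sections 3.4 and 3.5 make it secondary.

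**What to change.** In section 3.11, replace the logistic model for admission by a cause-specific hazard model for time to first heart-failure admission, censoring at death. This estimates the marker's effect on admission among patients still at risk, and it matches the hazard ratios in section 3.10. Report cumulative incidence with death as a competing event beside it, to describe absolute risk. The curve alone does not correct the marker effect, because it shows the same lower admission risk in a group that dies early.

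If logistic regression is kept, define the event as admission or death by a fixed time point, such as 3 or 5 years. A marker of death is then classed as high risk (odds ratio 2.06 to 3.55 in the table).

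The cost is a change of wording and slightly more analysis work. Admissions and deaths are already to be obtained from the registries, so no further data source is needed. The composite has the drawback of mixing two outcomes, so its components should also be shown separately.

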### 3.12 Data management

Data from patient's visit and patient's journal will be stored as de-identified data in an a password secured internet-based database (Viedoc). Viedoc is approved by The Norwegian Data Protection Authority for use in scientific studies. Echocardiographic data will be stored as de-identified DICOM files including locally performed measurements, labeled by the patient's study ID, all ECGs will be taken in digitalized format and be stored as de-identified image files as well as DICOM files. All de-identified files will be locally stored at a dedicated server. Key files coupling personal patient information to ID's will be stored locally on a server with restricted access. All de-identified ECGs, echocardiography-studies and key-files will be centrally collected at University Hospital of North Norway, Tromsø, latest after end of the second patient's visit. Echocardiographic data will be analyzed in the core-lab at University Hospital of North Norway, Tromsø. Readers of the strain-data will be blinded for the outcome-data. Other researchers assess outcome-data from NPR and The Norwegian Cause of Death Registry will be added to the database. The de-identified dataset and DICOM images from echocardiography and ECG will also be transferred to NTNU Trondheim for automated reading of the echocardiographic imaging and AI purposes.

## 4 Plan for activities, visibility and dissemination

Data collection will start after final Regional Ethics Committee (REK) and Data Protection Officer (PVO) approval. A long-term follow-up of at least 5 years, possibly 10 to 15 years is planned after an inclusion period of at least 2 years plus one-year clinical control. A core-lab will be established in Tromsø for analyses of all echocardiographic measurements and post-processing. University Hospital of North Norway, Tromsø will coordinate and assess the quality of data acquisition and database from the different centers. All registry-data from NPR and The Norwegian Causes of Death Registry as follow-up data will be retrieved by a dedicated research administrator.

